**Definition of Baseline:**

The last non-missing measurement prior to the randomization date will be used as the baseline measurement. Definition of baseline will be used for all efficacy analysis.

**Definition of pre-treatment value:**

The last non-missing measurement prior to the first trial drug administration will be used as the pre-treatment baseline measurement. Definition of pre-treatment value will be used as baseline for all safety analysis.

**Definition of duration:**

Duration (in days) will be calculated by the difference between start and stop date + 1, unless otherwise specified.

**Conversion factors:**

The following conversion factors will be used to convert days into weeks or months or years, or vice versa:

- 1 week = 7 days
- 1 month = 30.4375 days
- 1 year = 365.25 days

**Handling of missing data:**

Unless otherwise specified (Sections 13.1, 13.3, 14.2, 16.1.1, 17.1), missing data will not be replaced.

In all subject data listings imputed values will be presented. In all listings imputed information will be flagged.

Missing statistics, e.g., when they cannot be calculated, should be presented as “nd”. For example, if n=1, the measure of variability (Sd) cannot be computed and should be presented as “nd”.

**Software:**

All statistical analyses will be performed using SAS® software version 9.2 or higher.

## 12 Trial Subjects

The subsections in this section include specifications for reporting subject disposition and treatment/trial discontinuations. Additionally, procedures for reporting protocol deviations are provided.

### 12.1 Disposition of Subjects and Discontinuations

Descriptive statistics will be used to summarize subject disposition and reason for discontinuation, based on the electronic case report form (eCRF) data.

The following information will be reported:

- Number of subjects screened.
- Number of subjects who discontinued from the study prior to randomization, overall and grouped by reason (i.e. Subject did not meet all eligibility criteria, Withdrew informed consent, Progressive disease, Adverse event, Lost to follow-up, Death, Other as reported on the “Study Entry” eCRF page).
- Number of randomized subjects in each treatment arm
- Number of randomized subjects who received no treatment in each treatment arm
- Number of randomized subjects ongoing on treatment in each treatment arm (subject initiated one or more treatment as reported on the “Cetuximab Administration”, “Cisplatin Administration”, “Carboplatin Administration” and “5-FU Administration” eCRF page and at least one of initiated treatments is not discontinued as reported on the “Cetuximab Termination”, “Cisplatin Termination”, “Carboplatin Termination” and “5-FU Termination” eCRF pages)
- Number of randomized subjects who are off treatment in each treatment arm and reason for treatment discontinuation. To be accounted as off all treatments a subject must discontinue all the initiated treatments (as reported on the “Cetuximab Termination”, “Cisplatin Termination”, “Carboplatin Termination” and “5-FU Termination” eCRF pages). If the treatments are discontinued for different reasons, the reason for discontinuation of the last treatment will be taken into account.
- Number of randomized subjects who discontinued the treatment after randomization, grouped by treatment arm and main reason separately for each treatment component (as reported on the “Cetuximab Termination”, “Cisplatin Termination”, “Carboplatin Termination” and “5-FU Termination” eCRF pages). For cisplatin, the number of randomized subjects who definitely discontinue cisplatin and number of those who switched to carboplatin will also be displayed.
- Number of randomized subjects who stopped assessments grouped by treatment arm and main reason (as reported on “End of Assessment Visit” eCRF page)
- Number of randomized subjects who continued only in survival follow-up after randomization, grouped by treatment arm (subjects who discontinued/completed all treatments and have no evidence of study discontinuation as reported on “Study Termination” eCRF page)

- Number of randomized subjects who discontinued the trial after randomization, grouped by treatment arm and main reason (as reported on “Study Termination” eCRF page)
- The results of the randomization algorithm (according to IWRS) will be summarized as follows:
  - Number of randomized subjects by randomization strata (IWRS)
  - Number of randomized subjects by randomization strata (eCRF)
  - Cross tabulation: stratum by IWRS vs. stratum by CRF
  - Cross tabulation: subjects randomized (A/B/no) vs. treated (A/B/no)

In addition, a summary table will be provided displaying the number and percentage of subjects by site for each analysis set.

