Tumor assessment: Tumor assessment will be performed according to RECIST version 1.1. The baseline tumor assessment is to be performed during the screening period within 28 days before the start of trial treatment. Computed tomography (CT) or magnetic resonance imaging (MRI) with contrast enhancement is recommended for tumor assessment. Subsequent tumor response evaluations will be assessed every 6 weeks (± 3 days) starting from the randomization day until occurrence of PD regardless of any cycle delay. If treatment is discontinued for reasons other than PD, subjects will continue to have tumor assessments until either PD, the start of a new antitumor treatment, death, the termination of the trial, or loss of follow up, whichever comes first. If symptoms are suggestive of PD, subjects will be evaluated by imaging studies thereafter for documentation and confirmation of the tumor responses. The details of documentation of tumor assessment is described in Section 7.3.1.

Safety follow-up period: All subjects in Arm A and B will be followed up continuously for safety evaluations according to schedule of assessments in Table 1.1 starting from date of first signature of informed consent. A Safety Follow-up visit will be performed 30 days (± 3 days) after the last dose of trial treatment or immediately before starting any new antitumor treatment. During the treatment period, additional safety evaluations will be on a weekly basis (Arm A only) for physical examination, vital signs, documentation of AEs and concomitant medications, and also at the start of each cycle (for both arms) for ECOG performance status, ECG, hematology, biochemistry and urinalysis. Survival data and any information on new antitumor treatments will be collected every 3 months after the EOEA visit until either death, loss of follow up, or the termination of the trial, whichever comes first.

Primary and secondary endpoints: The primary endpoint of this trial is PFS time, as assessed by an IRC. Secondary endpoints include PFS time, as assessed by the Investigator, OS time, BOR rate, DCR, duration of response, and safety (see Section 8).

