5.4 Criteria for Subject Withdrawal

5.4.1 Withdrawal from Trial Therapy

A subject must be withdrawn from all trial treatment (cetuximab and chemotherapy) in the event of any of the following but should stay in the trial:

- Occurrence of an exclusion criterion that is clinically relevant and affects the subject's safety and discontinuation is considered necessary by the Investigator and/or Sponsor.
- Occurrence of AEs and discontinuation of trial treatment is desired or considered necessary by the Investigator and/or the subject.
- Occurrence of pregnancy during trial treatment.
- Occurrence of PD according to RECIST version 1.1.

Document No. CCI	
Object No.	

- Intake of prohibited medications, as defined in Section 6.5.2, if deemed necessary by the Investigator and/or Sponsor.
- Non-compliance.

In case of premature withdrawal from the trial treatment for reasons other than PD, the subjects will be asked to attend scheduled visits until an assessment of PD as planned.

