7.1.7 Survival Follow-Up

The following assessments will be performed every 3 months after the EOEA visit until death or termination of the trial, whichever comes first. This follow-up can take the form of a telephone contact to the subject or the subject's family, or their referring doctor.

- Survival status.
- Documentation of subsequent antitumor treatment after the end of trial treatment.
- Outcome and resolution date of skin reactions.
- Resolution of ongoing SAEs (see Section 7.4.1.6).

Document No. CCI
Object No.

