All subjects in Arm A and B will be followed up continuously for safety evaluations according to schedule of assessments in Table 1.1 of the protocol, **Error! Reference source not found.** starting from date of first signature of informed consent. A Safety Follow-up visit will be performed 30 days ( $\pm$  3 days) after the last dose of trial treatment or immediately before starting any new antitumor treatment. During the treatment period, additional safety evaluations will be on a weekly basis (Arm A only) for physical examination, vital signs, documentation of adverse events and concomitant medications, and also at the start of each cycle (for both arms) Eastern Cooperative Oncology Group (ECOG) performance status, electrocardiogram (ECG), hematology, biochemistry and urinalysis. Survival data will be collected every 3 months after the end of efficacy assessment (EOEA) visit until either death, loss of follow up, or the termination of the trial, whichever comes first.

The trial will be terminated when the last subject has discontinued the trial treatment or OS cut-off, whichever is later. After OS cut-off and before the trial termination, only SAEs during treatment and at the EOEA visit will be reported, following the usual reporting procedure. Information collected in the EOEA forms will be limited to data on date of trial treatment completion, date of last treatment, subject status at end of trial, reason for discontinuation, disease progression (yes/no). From alive, but trial-treatment-discontinued subjects, no tumor response data, anti-cancer treatment and survival information will be collected.

**Planned number of subjects:** 240 subjects.

**Primary endpoint:** The primary endpoint is PFS time, as assessed by an IRC.

**Secondary endpoints:** The secondary endpoints include PFS time, as assessed by the Investigator, OS time, BOR rate, DCR, duration of response, and safety.

**Pharmacokinetics:** Not applicable.

**Other assessments:** Not applicable.

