**Planned treatment duration per subject:**

The treatment duration per subject may vary. Subjects will be treated with a maximum of 6 cycles of chemotherapy and/or cetuximab weekly in the absence of PD, as assessed by the Investigator, and unacceptable toxicity. Subjects (in Arm A) who demonstrate at least a tumor

response of stable disease (RECIST version 1.1) after 6 cycles of trial treatment will continue monotherapy with cetuximab until either PD or occurrence of unacceptable toxicity. Subjects who stop treatment before reaching PD will continue to have tumor assessments (CT or MRI) every 6 weeks until either PD, the start of a new antitumor treatment, death, or termination of the trial, or loss of follow up, whichever comes first. Upon occurrence of PD, all trial treatments should be discontinued.

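### SAP 12.1 counts subjects who are off treatment but still being scanned as being in survival follow-up only; the rule for this descriptive row needs an end-of-assessment condition

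*SAP*

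**What the plan says.** SAP 12.1 lists, among the disposition outputs, "Number of randomized subjects who continued only in survival follow-up after randomization, grouped by treatment arm". The parenthesis that follows defines the row as "subjects who discontinued/completed all treatments and have no evidence of study discontinuation as reported on" the Study Termination eCRF page. That makes two conditions: off all treatment, and no study termination recorded.

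Another row in the same section is the "Number of randomized subjects who stopped assessments grouped by treatment arm and main reason", taken from the End of Assessment Visit eCRF page.

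On imaging after treatment, Protocol 5.1 states: "If treatment is discontinued for reasons other than PD, subjects will continue to have tumor assessments until either PD" or another listed end (new antitumor treatment, death, trial termination, loss to follow-up). Protocol 5.4.1 adds that after early withdrawal from treatment for reasons other than progression "the subjects will be asked to attend scheduled visits until an assessment of PD as planned". SAP section 6 (planned treatment duration) repeats it: "Subjects who stop treatment before reaching PD will continue to have tumor assessments (CT or MRI) every 6 weeks until either PD" or one of the same other ends.

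On when survival follow-up starts, Protocol 7.1.7 says "The following assessments will be performed every 3 months after the EOEA visit until death or termination of the trial", and SAP section 6 (Methodology) says "Survival data will be collected every 3 months after the end of efficacy assessment (EOEA) visit". Footnote 3 of Protocol Table 1.1 ties the EOEA visit to the day on which efficacy follow-up is judged to be over.

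**The concern.** The trial has two states after treatment. In the first, the subject is off drug and still imaged every 6 weeks. In the second, which begins after the EOEA visit, only survival, later therapy and a few safety outcomes are collected. The label of the SAP row describes the second state. Its rule captures both.

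The two arms do not pass through the first state equally. An Arm B subject with stable disease or a response after cycle 6 has completed all treatment and falls into the row while still being scanned. The comparable Arm A subject stays on cetuximab until progression or unacceptable toxicity and is counted as on treatment. Arm A subjects enter the row wrongly only if they stop every drug without progression. A by-arm count that is wrong mainly in the control arm is worth correcting in a trial whose primary endpoint is imaging-based PFS, even though the table is only descriptive.

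**Working it through.** **Comparing the definitions.** Take an Arm B subject who has finished 6 cycles, has stable disease, has started no new therapy and has not left the trial.

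| Source | Where the subject belongs |
|---|---|
| Protocol 5.1 and 5.4.1; SAP 6 | 6-weekly tumor assessments continue |
| Protocol 7.1.7 and Table 1.1 footnotes 3 and 5; SAP 6 | No EOEA visit yet, so survival follow-up has not begun |
| SAP 12.1, stopped-assessments row | Not counted (no End of Assessment Visit page) |
| SAP 12.1, survival-follow-up row | Counted (all treatments completed, no Study Termination page) |

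The last line conflicts with the other three, and nothing else in the SAP adds the missing condition.

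**Scale.** The plan gives no figure to reproduce, and its sample size text is redacted. The following is an illustration and not trial data.

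Inputs:
- Arm B size: 240 subjects at 2:1, so 240/3 = 80 (Protocol synopsis).
- Control median PFS 3.3 months, from the earlier trial cited in Protocol 3.7.2; exponential shape assumed. Rate λ = ln 2/3.3 = 0.2100 per month.
- Six 21-day cycles = 126 days = 126/30.4375 = 4.14 months (month length from SAP 11).
- Uniform accrual over 24 months, in line with the anticipated recruitment period in Protocol 5.1 (fourth quarter of 2015 to fourth quarter of 2017).
- Scanning ends only at a PFS event; no early switch to new therapy and no loss to follow-up.

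The number of Arm B subjects past cycle 6, progression-free and still scanned at a cut-off g months after accrual ends is

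(80/24)/λ × [exp(−λ·max(4.14, g)) − exp(−λ·(24+g))], with (80/24)/λ = 15.87.

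| g (months) | Bracket | Subjects |
|---|---|---|
| 0 | 0.4191 − 0.0065 | 6.5 |
| 3 | 0.4191 − 0.0034 | 6.6 |
| 6 | 0.2836 − 0.0018 | 4.5 |
| 12 | 0.0804 − 0.0005 | 1.3 |

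The 12-month line is the latest OS cut-off that SAP section 8 allows.

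**Sensitivity to accrual.** Setting the cut-off at the expected 144th PFS event instead (medians 3.3 and 5.6 months, no censoring), and taking treatment to end at day 126 or at day 110 (the last planned 5-FU day), gives 6.5 to 7.2 Arm B subjects with 24-month accrual, 8.3 to 9.3 with 18-month and 11.3 to 12.8 with 12-month accrual. Faster accrual raises the count because more subjects are recent at the cut-off.

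Arm A is not quantified: the documents give no rate of stopping all drugs without progression.

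**The case against.** The strongest reply is that little depends on this row.

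- The stopped-assessments row in the same section is correct. A subject still being scanned has no End of Assessment Visit page and is not counted there.
- Subtracting that row from the number off all treatment roughly recovers the missing group, apart from cases such as never-treated subjects.
- PFS follow-up is reported elsewhere. SAP 16.1.1 gives event and censoring categories by arm, a listing with last tumor assessment dates, and a plot of planned against actual assessment days by arm. SAP 16.3 gives a follow-up duration by inverted censoring of investigator-assessed PFS.
- The PFS derivation, its censoring rules and the Cox model do not use the row.

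All of this stands, and it rules out stronger readings. A reader might infer that control subjects still followed for the primary endpoint will be reported as no longer assessed, or that completeness of follow-up for IRC-assessed PFS is misstated by arm. The outputs above do not support either. Nor is it right that the row cannot be reconciled with its neighbor, since the disagreement can be seen and largely worked out. The open-label design adds nothing here: the IRC review is blinded (Protocol section 2), and the row involves no assessor's judgment.

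One might also quote the share of Arm B still progression-free at 126 days, exp(−0.2100 × 4.14) = 0.419, or about 34 of 80. That counts everyone who ever passes through the state, whereas a disposition table is a snapshot at a cut-off.

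The objection does not make the row's own rule right. As written it gives a count that contradicts its label.

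**Conclusion.** The point holds as a definitional error confined to one descriptive row. SAP 12.1 counts as survival follow-up only a group that both documents keep under 6-weekly imaging. The excess is expected to be larger in Arm B; that direction follows from the treatment rules and has not been quantified against Arm A, which is twice as large.

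Under the assumptions shown, about 4 to 7 Arm B subjects would be miscounted at a cut-off 0 to 6 months after accrual ends and about 1 at 12 months. Switches to new therapy or loss to follow-up before progression would lower these counts; stopping all treatment early without progression would raise them. The conclusion rests on the definitions and not on the counts.

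The importance is low: no efficacy result changes.

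**What to change.** In SAP 12.1, define the row by three conditions: all treatments discontinued or completed, End of Assessment Visit page completed, and no Study Termination page. Add one row by arm for subjects off treatment with tumor assessments ongoing: all treatments ended, no End of Assessment Visit page, no Study Termination page.

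This assumes that the End of Assessment Visit page is the record of the EOEA visit. That is a reasonable reading, but the eCRF is not among the documents, so it should be confirmed first. The cost is one sentence and one table row, from pages the SAP already uses. No new data are needed and no other analysis changes.

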## 12.2 Protocol Deviations

### 12.2.1 Important Protocol Deviations

The following summary tables and listings of important protocol deviations will be provided (separately for pre-/post inclusion deviations):

- Frequency table per reason of important protocol deviations
- Listing of important protocol deviations

Relevant protocol deviations post-inclusion will be determined by either medical review processes or by programming (See [Appendix 1](#) for detailed specifications).

### 12.2.2 Reasons Leading to the Exclusion from an Analysis Set

Subjects who meet at least one criteria described in section 10.2 will be excluded from the PP. For these subjects, each criteria will be summarized and listed;

- Frequency table per criteria

Listing of each criteria.

## 13 Demographics and Other Baseline Characteristics

Descriptive statistics will be used to summarize demographic and baseline characteristics, based on the eCRF data. Summaries will be performed on the ITT analysis set.

### 13.1 Demographics

Demographic characteristics will be based on the ITT analysis set and repeated on the PP and Safety analysis sets only if the PP set is less than 90% of ITT.

Demographic characteristics will be summarized as follows:

- Sex: Male, Female.
- Race: Asian, Other.
- Subject is Chinese: Yes, No
- Subject is Chinese citizen: Yes, No
- Age (years): summary statistics.
- Age categories: < 65 years, ≥ 65 years (further break-down: 65 - < 75 years, 75 - < 85 years, ≥ 85 years).
- Eastern Cooperative Oncology Group (ECOG) Performance Status at baseline: 0, 1, ≥2.
- Height (cm) at baseline: summary statistics.
- Nicotine consumption: summary statistics
- Alcohol consumption: summary statistics
- HPV status: positive/negative/unknown

Specifications for computation:

- Age (years): (date of given informed consent – date of birth + 1) / 365.25. The integer part of the calculated age will be used for reporting.
  - In case of missing day for at least one date, but month and year available for both dates:  
For the derivation of age, the day of informed consent and the day of birth will be set to 1 and the formula above will be used
  - In case of missing month for at least one date, but year available for both dates:  
For the derivation of age, the day and the month of informed consent and the day and month of birth will be set to 1 and the formula above will be used

A supportive listing will be provided.

## 13.2 Medical History

The summary tables for past and ongoing Medical History will also be provided detailing the number and percentage of subjects by Medical Dictionary for Regulatory Activities (MedDRA) primary System Organ Class (SOC) (ordered alphabetically) and Preferred Term (PT) (ordered alphabetically); each subject will be counted only once within each PT or SOC. The summaries will be based on ITT analysis set.

The related listing will also be provided.

## 13.3 Other Baseline Characteristics

Information on **disease characteristics** collected on the “Disease History” eCRF page will be summarized on ITT analysis set as follows:

- Site of primary tumor. The location of the tumor as reported on the “Disease history” eCRF page according to the International Classification of Diseases for Oncology (ICD-O) and the decoded term will be presented.
- Tumor histopathologic / cytologic type: Squamous cell carcinoma Well differentiated, Squamous cell carcinoma Moderately differentiated, Squamous cell carcinoma Poorly differentiated, Squamous cell carcinoma None.
- T stage at initial diagnosis: T0, T1, T2, T3, T4, TIS, TX.
- N stage at initial diagnosis: N0, N1, N2, N3, NX.
- M stage at initial diagnosis: M0, M1, MX.
- T stage at study entry: T0, T1, T2, T3, T4, TIS, TX.
- N stage at study entry: N0, N1, N2, N3, NX.
- M stage at study entry: M0, M1, MX.
- Time since initial cancer diagnosis (months), defined as (date of randomization – date of initial cancer diagnosis) / 30.4375: summary statistics.
  - Time since first occurrence of recurrent disease (months), defined as (date of randomization – date of first occurrence of recurrent disease) / 30.4375: summary statistics.
- Time since first occurrence of metastatic disease (months), defined as (date of randomization – date of first occurrence of metastatic disease) / 30.4375: summary statistics.
- Metastatic sites.

Handling of missing/incomplete dates for initial cancer diagnosis, documented, locally advanced, inoperable or metastatic disease diagnosis and for first occurrence of metastatic disease:

If only the day is missing, the date will correspond to the last day of the given month. If day and month are missing, the date will be set to the last day of the given year. The imputed date should not be later than the screening date.

A listing will support this table.

